SOP	Standard Operating Procedure
TIA	Transient ischemic attack
UB-92	Uniform Billing Code of 1992
US	United States
VMS	Vasomotor Symptom
VTE	Venous Thromboembolism

2. ABSTRACT

Title: Post-Authorization Safety Study (PASS) of conjugated estrogens/bazedoxifene (CE/BZA) in the United States

Protocol: Version 4.0 (Final), 20 July, 2015

Main author: [name]., Pfizer, Inc.

Rationale and background: Conjugated estrogens/bazedoxifene (CE/BZA) is authorized in the European Union (EU; as Duavive[®]) for the treatment of estrogen deficiency symptoms in postmenopausal women with a uterus (with at least 12 months since the last menses) for whom treatment with progestin-containing therapy is not appropriate. It is expected to be commercially available in the EU in 3Q/4Q 2015. In the United States (US), the product, approved as Duavee[®] by the Food and Drug Administration (FDA), has been commercially available since May 2014 for use in women with a uterus for the treatment of moderate to severe vasomotor symptoms (VMS) associated with menopause and for the prevention of postmenopausal osteoporosis. It is important to collect as much real-world safety data as possible regarding actual use in the populations for which the product is prescribed. This protocol describes a non-interventional study (NIS) designated as a Post-Authorization Safety Study (PASS) that will be conducted in the US in order to fulfill a post-authorization commitment to the European Medicines Agency (EMA).

Research question: The overall aim of this PASS is to monitor the safety profile of *Duavee* in comparison to estrogen + progestin (E+P) combination hormone replacement therapies (HRT) in the US.

Objectives:

- Primary objective: to estimate the incidence and compare the risk of endometrial hyperplasia and endometrial cancer among postmenopausal women initiating *Duavee* and postmenopausal women initiating E+P HRT.
- Secondary objective: to estimate the incidence and compare the risk of selected secondary safety endpoints listed in [Section 7.3.2.2](#) among postmenopausal women initiating *Duavee* and postmenopausal women initiating E+P HRT.

Study design: This PASS is a retrospective cohort study utilizing a US healthcare claims data source (HealthCore Integrated Research DatabaseSM [HIRD]). Two treatment groups of new initiators (*Duavee* and E+P HRT) will be defined and followed for each specified endpoint until the end of the study period or until that endpoint occurs. Other censoring events include hysterectomy, switch of index treatment, and disenrollment from the HIRD, diagnosis of cancer or death. The planned study will be 4 years in duration and will follow new initiators identified in 2014-2018.

Study Population: All patients identified in the HIRD who have received at least one prescription for *Duavee* or E+P HRT since May 2014 (US commercial launch date), and have a baseline period (e.g., 6 or 12 months to be determined by a priori analyses) prior to their first study medicine prescription, will be included in this study. Patients without a uterus and those with an existing cancer diagnosis will be excluded. Only new initiators will be included in the main analysis. To be a new initiator, patients need to have no recorded use of either *Duavee* or E+P HRT products in their baseline period. Patients with prior use of E+P HRT in either the *Duavee* or E+P HRT cohort will be excluded from the main analyses, but will be included in sub analyses. Similarly, patients with a history of unopposed estrogen use in their baseline period will be analyzed in sub analyses but excluded from the main analyses. Figure 4 in [Section 7.7](#) details the analysis populations.

Variables: Variables will be defined and analyzed that represent patient characteristics, comorbidities, utilized medications, medical history, and safety endpoints. A listing of study variables is provided in [Section 7.3.1](#).

Data source: The HIRD is a longitudinally integrated, US research database comprising payment claims for healthcare encounters among included health insurance plans. It is among the largest of its kind in the US and has been extensively used for pharmacoepidemiologic research, including many PASS.^{1,2,3,4}

Automated data from the HIRD will be linked to the US National Death Index (NDI) to ascertain mortality endpoints, including all-cause mortality and mortality specific to study endpoints of interest. Medical records (for a random sample of 400 potential cases) will be used to refine and validate algorithms for identification of the primary endpoints (endometrial hyperplasia and endometrial cancer). For development of the endometrial endpoint algorithms, clinical evidence available in the medical record, which includes all results of endometrial biopsies and clinician evaluations, will be considered the gold standard definition of case status against which the claims-based algorithm's performance will be measured.

Study size: Hazard ratios (HRs) and their 95% confidence intervals (CIs) expected to be observed in this study were estimated. Endometrial hyperplasia and endometrial cancer are defined as the primary endpoints and were used for these calculations. The number of *Duavee* users in HIRD during the study period has been projected based on Pfizer commercial forecasts only; no patient data are currently available. Estimates of E+P HRT use were obtained based on pilot analyses of the HIRD from the last three years. For Year 1 of the US PASS, the 95% CI of the HR for the risk of endometrial hyperplasia is projected to lie between 0.44 and 2.26 (assuming the true HR=1.0) indicating that the study would be able to rule out an HR greater than 2.26. For Years 2 and 3, the CIs for endometrial hyperplasia risk in the study is projected to lie between (0.64 and 1.56), and (0.72 and 1.39), respectively. This indicates that the study would be able to rule out an HR greater than 1.56 at two years and greater than 1.39 at three years.

Data analysis: Analyses will focus on the comparison between women initiating either *Duavee* or E+P HRT. Baseline characteristics will be compared across the two cohorts of new users to assess potential confounding variables. For each safety endpoint (venous thromboembolism [VTE], stroke, coronary heart disease [CHD], breast cancer, ovarian cancer, endometrial hyperplasia, and endometrial cancer, etc.), univariate and adjusted HRs will be estimated that compare incidence of the first occurrence of each safety event between *Duavee* and E+P HRT users.

Milestones: Three (3) annual interim study reports and a final report will be submitted to the EMA/Committee for Medicinal Products for Human Use (CHMP) cumulatively covering patients in the HIRD who initiate *Duavee* or E+P HRT in 2014-2015 (interim report 1), 2015-2016 (interim report 2), 2016-2017 (interim report 3) and 2017-2018 (final report). In addition to data on new initiators, each report will also contain cumulative data on the entire cohorts. Due to an 18 to 24-month lag time for availability of mortality data through the NDI, a mortality supplement to the final report will also be provided approximately two years after the final study report, to capture death endpoints over the full study period.

3. AMENDMENTS AND UPDATES

None.

4. MILESTONES

Milestone	Planned date
Updated FULL Draft Protocol submitted to CHMP/PRAC	10 October 2014
FINAL Draft Protocol Submission to EMA (for PRAC review)	26 January 2015
Update to FINAL Protocol in response to PRAC assessment	23 July 2015

Protocol Registration in the EU PAS register (upon endorsement from the PRAC/CHMP)	01 October 2015
Start of data collection ^a	01 May 2014
End of data collection ^b	01 May 2018
1 st Annual Study Report ^c	31 March 2016
2 nd Annual Study Report	31 March 2017
3 rd Annual Study Report	31 March 2018
FINAL Study Report	31 March 2019
Mortality Supplement to the FINAL Study Report	31 March 2021 ^d

a. This is a retrospective cohort study and the source data has been accruing since *Duavee* became available in the US in May, 2014. In accordance with EU Pharmacovigilance Guidance (Module VIII), the start of a PASS using secondary data is defined to be when the analytic dataset is extracted. This will not be done until the study protocol has been approved by the PRAC.

b. Study Period is from May 2014 through May 2018.

c. Time from US launch (May 2014) to First Annual Report is 23 months: 12 months is needed to accumulate one year of observation, a database lag of 4 months from real-time, and 7 months needed to extract data, perform analyses, and generate submission ready First Annual Report.

d. National Death Index data lags real-time by 18-24 months and is updated only once annually. Mortality follow-up will end May, 2018. See Figure 2 for further details.

CHMP = Committee for Medicinal Products for Human Use; EMA = European Medicines Agency; PAS = Post Authorization Studies; PRAC = Pharmacovigilance Risk Assessment Committee.

5. RATIONALE AND BACKGROUND

In the EU, CE/BZA (authorized as *Duavive* 0.45 mg/20 mg modified-release tablets) is indicated for the treatment of estrogen deficiency symptoms in postmenopausal women with a uterus (with at least 12 months since the last menses) for whom treatment with progestin-containing therapy is not appropriate.

In the US, CE/BZA (authorized as *Duavee*) is indicated for use in women with a uterus for the treatment of moderate to severe VMS associated with menopause; and for the prevention of postmenopausal osteoporosis. *Duavee* has been commercially available in the US since May 2014, and is planned to be made commercially available in the EU during 2015. Compared to the EU, the US indication for *Duavee* is broader (i.e., not restricted to those whom progestin-containing treatment is inappropriate, and indicated for osteoporosis prevention). Therefore, it is anticipated that by conducting the PASS in the US, the population of women who would be indicated for *Duavive* in the EU will also be adequately

represented. This study will collect real-world data on the risks of various endpoints among populations for which the product is prescribed. Because *Duavee* is an estrogen-containing product, endometrial hyperplasia and endometrial cancer are relevant safety events and have been designated as primary safety endpoints, while all other safety events are secondary endpoints.

This PASS is designed to provide interim reports at regularly scheduled intervals over the duration of the study. The rationale for conducting the study in a US population is to draw from the broader patient population indicated for *Duavee*, as well as to achieve large study samples sooner than would be possible if the study were to rely on data obtained from the EU. These advantages are based on the earlier launch of the product in the US as compared to the EU, and the large size is due to the greater sample sizes accessible in US healthcare data sources.

This protocol describes a NIS designated as a PASS that will be conducted in the US as a post-authorization commitment to the EMA.

6. RESEARCH QUESTION AND OBJECTIVES

6.1. Research Question

The overall aim of this PASS is to monitor the safety profile of *Duavee* (CE/BZA) in comparison to E+P combination HRTs.

6.2. Objectives

[figure not shown]
- Primary objective: to estimate the incidence and compare the risks of endometrial hyperplasia and endometrial cancer among postmenopausal women initiating *Duavee* and postmenopausal women initiating E+P HRT during the first four years of *Duavee* availability in the US (2014-2018)
- Secondary objective: to estimate the incidence and compare the risks of selected safety endpoints listed in [Section 7.3.2](#), among postmenopausal women initiating *Duavee* and postmenopausal women initiating E+P HRT.

7. RESEARCH METHODS

7.1. Study Design

This PASS is a retrospective cohort study utilizing a healthcare claims data source (HIRD) in the US. Two (2) treatment groups (*Duavee* and E+P HRT) will be identified, followed, and reported upon using annual database updates. A new-user cohort design will be used for the main analysis and users with a history of (E+ P) HRT will be examined in sub-analyses. The study will accumulate data for 4 years (May, 2014-May, 2018) as it follows a dynamic cohort of patients that enter the study at different times, based on when *Duavee* or E+P HRT is initiated.

Figure 1 shows the length of study follow-up according to when new users enter the cohort.

The study duration was determined based on sample size calculations, and is the soonest that clinically meaningful HRs for endometrial hyperplasia and endometrial cancer can be detected. Study years and reporting intervals will run from May 1 through April 30 of the next year. Interim (follow-up) and final reports will contain both interval and cumulative data.

All patients in the HIRD who initiate *Duavee* or E+P HRT in the study period (2014-2018) will be considered for inclusion. This PASS is a retrospective cohort study using secondary data. The source data has been accruing since *Duavee* became available in the US in May, 2014. In accordance with EMA Pharmacovigilance Guidance (Module VIII)⁵, the start of a PASS using secondary data is defined to be when the analytic dataset is extracted. This will not be done for this PASS until the study protocol has been approved by the PRAC.

Follow-up will continue from the first use of *Duavee* or E+P HRT through to the earliest of the following censoring events:

- End of continuous health plan eligibility;
- Switch from *Duavee* to an E+P HRT medication or vice-versa;
- (Note: Any use of an estrogen or estrogen-containing product (Appendix 2) that differs from the HRT treatment regimen dispensed on the index date will censor follow-up. This does not include dispensing of a topical estrogen that is a single-unit

E+P HRT. As described in [Section 7.7.4](#), sensitivity analyses exploring the impact of this criterion will be performed.

- First occurrence of a safety endpoint.
 - Once a patient has had a safety event, they will be censored from the analysis of that event only. For example, a patient for whom an endometrial hyperplasia outcome is identified will remain in follow-up for analysis of breast cancer (and endometrial cancer).
- End of the study period.
 - Patients will be censored by the end of the study period for each interim report and the final study report, however, additional follow-up time for these patients will be added during the subsequent study year.
- Occurrence of any type of cancer diagnosis;
 - As described in [Section 7.7.4](#), sensitivity analyses exploring the impact of this criterion will be performed.
- Hysterectomy;
 - Codes indicating a procedure for hysterectomy will be used to define this censoring criterion.
 - Presence of a code indicating post hysterectomy status (ICD-9-CM V88.01) or a hysterectomy procedure code at any time in the baseline or follow-up period will result in exclusion of the patient. The one exception is, when in the follow-up period, the procedure code precedes the hysterectomy status code (i.e., date of post-index hysterectomy is known); the patient's follow-up will be included, but censored on the procedure date.
- Death.

Discontinuation and/or resumption of *Duavee* or E+P HRT treatment will be defined and recorded, but follow-up will not be censored based on treatment discontinuation. Sensitivity analyses will be conducted to examine the impact of censoring based on (1) treatment switch and (2) cancer diagnosis. The Sponsor will also conduct sub-analyses for patients not included in the main analyses. These patient groups are those with either (1) use of E+P HRT (i.e., not new initiators), or (2) unopposed estrogen in their baseline period.

For each of the 4 study years, the Sponsor will: (1) identify and follow new *Duavee* or E+P HRT users; and (2) extend the follow-up to include newly available data covering any additional follow-up period for patients that were identified during previous study years.

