7.7.4. Sensitivity Analyses

Three sensitivity analyses are planned to explore the impact of censoring due to treatment switch, censoring from analyses of safety endpoints due to occurrence of any cancer type, and potential misclassification of the primary endpoints based on use of the developed algorithms.

Specifically, the main analyses for the primary and secondary endpoints will be performed including person-time after treatment switch, and the main analysis for the primary endpoints only (endometrial hyperplasia and endometrial cancer) will be performed including patients who had been censored due to cancer occurrence. The IR estimate for each primary outcome (endometrial cancer and endometrial hyperplasia) will be corrected for the PPV of the outcome algorithm as identified through validation. This will be done by multiplying the number of observed cases by the PPV point estimate, and will be presented with a 95% CI.

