
Hypertension
	
401.xx-405.xx, 437.2x, V81.1x
	
CPT: 3077F, 3080F

Breast Pain
	
611.71
	

Diabetes
	
250.xx (Type 1: 250.x1, 250.x3; Type 2: 250.x0, 250.x2)
	

Renal Disease	403.01, 403.11, 403.91, 404.02, 404.03, 404.12, 404.13, 404.92, 404.93, 582.xx, 583.0x-583.7x, 585.xx, 586.xx, 588.0x, V42.0x, V45.1x, V56.xx	
Osteoarthritis	715.xx	
Osteoporosis	733.0x, V82.81	
Major Depression	296.2x, 296.3x, 311.xx, V79.0x	HCPCS: G8959, G8960, G8126, G8127, G9193-G9195, CPT: 3088F-3093F
History of VTE/CVA/CHD Event	415.1x, 451.11, 451.19, 451.2x, 451.81, 453.8, 414.xx, 430.xx-438.xx, V12.51-V12.54	
History of Breast, Ovarian, or Endometrial Malignancy	174.xx, 198.81, V10.3x, 198.6x, 183.0x, 236.2x, 182.0x, 198.82, V10.43, V10.42	19120, 58950-58954, 58956-58958, 58960

Family history of cancer	V16.xx	
Hysterectomy	V88.01, V88.02	ICD-9-CM procedure: 68.4x-68.7x CPT: 58150-58294

Potential Algorithms for Claims-Based Identification of Safety Endpoints*

Event	Algorithm
Endometrial Cancer	To be determined via validation
Endometrial Hyperplasia	To be determined via validation
Venous Thromboembolism	Hospitalization with any of the following ICD-9-CM diagnosis codes listed as the principal discharge diagnosis: 415.1x, 451.11, 451.19, 451.2x, 451.81, 453.8x
CHD (i.e. MI, fatal MI, and Sudden Death)	MI defined as a hospitalization with ICD-9-CM code 410.xx (excluding 410.x2) with either (1) a length of stay between 3 and 180 days or (2) discharge status indicating death if length of stay is less than 3 days.
Stroke/TIAs	Hospitalization with ICD-9-CM diagnosis codes 433.x1, 434.x1, 436.x, 437.x1, 437.9x with either (1) a length of stay between 3 and 180 days or (2) death if length of stay is less than 3 days, or hospitalization with a principal discharge diagnosis of 435.xx (TIA)
Breast Cancer	At least two outpatient or one inpatient ICD-9-CM diagnosis code(s) 174.xx.
Ovarian Cancer	At least two outpatient or one inpatient ICD-9-CM diagnosis code(s) 183.0x.

Thyroid Cancer	Thyroidectomy during follow-up and ≥ 2 ICD-9-CM 193.xx diagnosis codes recorded.
Renal Cancer	At least two outpatient or one inpatient ICD-9-CM diagnosis code(s) 189.x
Renal adenoma	At least two outpatient or one inpatient ICD-9-CM diagnosis code(s) 223.x
Gastrointestinal Tract Cancer	At least two outpatient or one inpatient ICD-9-CM diagnosis code(s) 150.x – 159.x

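### Hysterectomy ends follow-up for every endpoint, including those that do not need a uterus, and no planned sensitivity analysis tests this possibly informative censoring

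*Protocol*

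**What the plan says.** Section 7.1 runs follow-up from first use "through to the earliest of the following censoring events" and gives a single list. Hysterectomy is on it: "Codes indicating a procedure for hysterectomy will be used to define this censoring criterion". The abstract repeats the rule: "Other censoring events include hysterectomy, switch of index treatment, and disenrollment from the HIRD, diagnosis of cancer or death". Neither place limits it to the endometrial endpoints. The entry for a first safety event is different. It stops only the analysis of that event, and the protocol's example keeps a woman with hyperplasia under observation for breast cancer.

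A second sentence under the hysterectomy entry goes further. "Presence of a code indicating post hysterectomy status (ICD-9-CM V88.01) or a hysterectomy procedure code at any time in the baseline or follow-up period" leads to exclusion of the patient. The one exception is a follow-up procedure code that precedes a status code, in which case "the patient's follow-up will be included, but censored on the procedure date".

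Section 7.1 also states that "follow-up will not be censored based on treatment discontinuation". Section 7.7.4 says "Three sensitivity analyses are planned to explore the impact of censoring due to treatment switch", and adds cancer censoring (primary endpoints only) and misclassification of the primary endpoints. Sections 7.7.1 and 7.7.6.1 describe reasons for censoring by exposure group. Section 7.3.3 describes the National Death Index (NDI) search for patients censored by disenrollment.

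**The concern.** A censoring event should be unrelated to the risk of the endpoint, given what the analysis adjusts for. Hysterectomy may be a consequence of uterine disease, and uterine disease is the effect that this study was set up to detect. If the two treatments differ in hyperplasia or bleeding, they may differ in hysterectomy, and the secondary endpoints would then be censored differently in the two cohorts for a reason linked to treatment.

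Stopping treatment after surgery does not by itself justify the rule, because discontinuation does not censor. Starting another estrogen product already censors under the switch rule.

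At stake are the secondary incidence rates and hazard ratios. Under the literal exclusion sentence, some women's whole record is at stake, including any primary endpoint reached before surgery.

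**Working it through.** The protocol gives no figure that depends on this rule, so there is none to reproduce. The first three steps compare the text with itself; the last three show the possible size under stated assumptions.

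**1. Scope.** One list, earliest event, no limit by endpoint. Section 7.3.2 has two primary endpoints that need a uterus. The secondary endpoints named in that section (VTE, CHD, stroke, breast, ovarian, thyroid, renal and gastrointestinal neoplasms, any cancer, all-cause mortality) include many that can occur without one. All stop at the procedure date.

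**2. The exclusion sentence, case by case.**
- Follow-up procedure code, later status code: kept, censored at the procedure.
- Follow-up procedure code, no status code: excluded on the literal wording, although the date of surgery is known.
- Status code only, or status code before the procedure code: excluded.

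The second case makes entry depend on a post-index event and removes all prior person-time and events. The protocol's own gloss on the exception, that the surgery date is known, suggests that censoring was intended. The wording does not say so.

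**3. What is tested.** Section 7.1 names switch and cancer diagnosis; Section 7.7.4 names switch, cancer censoring and algorithm misclassification. None relaxes the hysterectomy rule.

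**4. Person-time lost.** Assume a constant hysterectomy rate h and T years of follow-up with no other censoring. The share lost is 1 − (1 − exp(−hT))/(hT). The protocol gives no h, so a range is shown.

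| h per year | T = 1 | T = 4 |
|---|---|---|
| 0.2% | 0.1% | 0.4% |
| 0.5% | 0.25% | 1.0% |
| 1% | 0.5% | 2.0% |
| 2% | 1.0% | 3.9% |

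Four years is the extreme. Mean E+P follow-up at the third report in Table 1 is 89,438/50,350 = 1.78 years.

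**5. Events lost.** Let fD and fE be the shares of an endpoint's events that fall on or after hysterectomy in the Duavee and E+P cohorts. With person-time nearly unchanged, the hazard ratio is multiplied by about (1 − fD)/(1 − fE).
- 10% and 30%: 0.90/0.70 = 1.29, or 0.78 the other way round.
- 0% and 20%: 1.25 or 0.80.
- 20% in both: no change in the hazard ratio, but each rate is about 20% too low.

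All these shares are assumptions.

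**6. Ovarian cancer.** Appendix 2 requires "At least two outpatient or one inpatient ICD-9-CM diagnosis code(s) 183.0x". Assume 20 to 40 cases per 100,000 person-years. At the third report, 5,400 Duavee users at the 10 months of Table 1 footnote a give 5,400 × 10/12 = 4,500 person-years and 0.9 to 1.8 cases. Even accrual without dropout would give at most about 5,400 × 1.5 = 8,100 person-years and 1.6 to 3.2 cases. Section 7.7.6.2 withholds a hazard ratio until each cohort has at least one event and the total is at least four. On 4,500 person-years the Poisson chance of no Duavee case is exp(−0.9) = 41% to exp(−1.8) = 17%. If a quarter of cases were lost it would be 51% to 26%; if half, 64% to 41%. This matters only if the qualifying code is dated on or after surgery, and the protocol does not state how same-day events are treated.

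**The case against.** The strongest defence is that the rule is a coherent definition of the population at risk. The product is indicated for women with a uterus, and Section 7.2.2 excludes women without one for all endpoints. Ending follow-up at hysterectomy also keeps perioperative VTE out of the comparison, and VTE is the important identified risk. This stands. A reader might infer that the rule serves no purpose for the secondary endpoints; the protocol does not support that, and the rule may remain as the main analysis. What does not follow is that it needs no test. Section 7.2.2 concerns hysterectomy before initiation, and no reason is given for applying the condition to later follow-up of non-uterine endpoints.

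The ovarian argument is also fairly contested. One inpatient code qualifies, and a case dated to the admission for surgery may count. CPT codes 58950–58954 and 58956–58958 sit under malignancy history in Appendix 2, outside the hysterectomy range 58150–58294, so some cancer operations may not trigger censoring. ICD-9 procedure codes 68.4x–68.7x, however, carry no cancer exemption. Ovarian exposure is therefore conditional.

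Reporting censoring reasons by cohort would show unequal hysterectomy rates, but would not show their effect on any endpoint.

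**Conclusion.** The point holds as a gap in the sensitivity analyses and a defect in the exclusion sentence. The overall loss of person-time is probably small: 0.4% to 3.9% over four years, resting on assumed rates of 0.2% to 2% per year.

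A reader might infer that the secondary hazard ratios are biased, or that ovarian cancer and mortality are understated. The documents do not establish either. Bias in the hazard ratio needs differential loss, and its size and direction cannot be derived from the protocol. Censoring removes person-time as well as events. Mortality follow-up is already cut by the separate cancer rule, so the hysterectomy rule is not the only cause of lost deaths. Ovarian cancer is the most exposed endpoint only if its qualifying code is dated on or after surgery. What can be said is that censoring of the secondary endpoints may be informative and that nothing planned would show whether it is.

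**What to change.** 1. Add to Section 7.7.4 a fourth sensitivity analysis that continues follow-up past a dated post-index hysterectomy for the secondary endpoints, with ovarian cancer and all-cause mortality named. Count events on the procedure date and show perioperative VTE separately.
2. Amend the exclusion sentence in Section 7.1 so that any dated post-index hysterectomy procedure leads to censoring rather than exclusion, whether or not a status code follows.
3. Include women censored at hysterectomy in the NDI search of Section 7.3.3 for this analysis.

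The cost is protocol wording, one extra run on claims data already held, and a few more NDI records. The downside is some post-surgical person-time in a secondary analysis. The main analysis keeps its hysterectomy censoring rule; item 2 only restores women who would otherwise be dropped.

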7.2.2. Exclusion Criteria

Patients meeting any of the following criteria will be excluded from the study:

- Patients with an insufficient period of enrollment prior to their index prescription (e.g., 6 or 12 months as determined prior to the start of analysis) will be excluded. This period is necessary to determine if the patient is a new initiator of *Duavee* or E+P HRT without a history of unopposed estrogen use, and also to adequately ascertain baseline covariates/patient history;
- Patients without a uterus, i.e., males, or women for whom evidence of hysterectomy is identified prior to initiation of *Duavee* or comparator E+P HRT; and
- Patients with a history of any type of cancer in their baseline period.
- Patients for whom *Duavee*, comparator E+P HRT or unopposed estrogen are identified during the baseline period will be excluded from the main analyses. They will be evaluated in separate sub-analyses.

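### Section 7.1, read literally, deletes women with a dated post-index hysterectomy unless a status code follows, and so contradicts its own censoring rule, the abstract and Section 7.2.2

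*Protocol*

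**What the plan says.** Section 7.1 follows each woman from first use "through to the earliest of the following censoring events", and hysterectomy is on that list. Two sub-points follow.

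- The first treats a procedure code as a reason to censor: "Codes indicating a procedure for hysterectomy will be used to define this censoring criterion".
- The second treats it as a reason to exclude. A post-hysterectomy status code (V88.01) "or a hysterectomy procedure code at any time in the baseline or follow-up period will result in exclusion of the patient". It then adds: "The one exception is, when in the follow-up period, the procedure code precedes the hysterectomy status code". A parenthesis explains that the date of the post-index surgery is then known, and such a patient's "follow-up will be included, but censored on the procedure date".

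Elsewhere, the abstract lists hysterectomy among the other censoring events. Section 7.2.2 excludes "women for whom evidence of hysterectomy is identified prior to initiation of" a study treatment and says nothing about hysterectomy afterwards. Appendix 2 lists two status codes for hysterectomy, "V88.01, V88.02", whereas Section 7.1 names only the first. For both primary endpoints, Appendix 2 gives the algorithm as "To be determined via validation". None of the three sensitivity analyses in Section 7.7.4 concerns hysterectomy.

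**The concern.** A woman who has a hysterectomy after her index date and never acquires a status code does not meet the stated exception. As written, she leaves the cohort altogether. Her person-time goes, and so does any endometrial hyperplasia or cancer recorded before the operation.

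This is selection on post-index information. It matters more here than for most events because hysterectomy can be the treatment for the two primary endpoints. That is general clinical reasoning; the protocol gives no figure for how often it happens. Women with the endpoint would then be more likely than others to be deleted. The primary objective is to estimate incidence as well as to compare risk, so a loss of cases matters even when it is equal in the two cohorts.

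The rule is also unstable over time. Section 7.1 extends follow-up each year and reports cumulatively. A case counted in one report could vanish from the next once the surgery is coded, and return later if a status code appears.

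A second, weaker point concerns women who are kept. Censoring on the surgery date could drop a case first identified on or after that date, depending on how the event is dated.

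**Working it through.** **Step 1. Set the rules side by side for a woman with no pre-index evidence of hysterectomy.**

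| Post-index codes | Exclusion sentence in 7.1 | Censoring sentence in 7.1, abstract, 7.2.2 |
|---|---|---|
| Procedure, then status code | Kept, censored at procedure | Kept, censored at procedure |
| Procedure, no status code | Excluded | Kept, censored at procedure |
| Status code, no procedure code | Excluded | Not addressed (surgery undated) |

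The rules conflict in the second row. The surgery date is known there, because the procedure code supplies it, so the reason given in the parenthesis applies equally to the first and second rows.

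The term follow-up period does not rescue the sentence. In the exception, the status code comes after the procedure date, which is the date on which the woman is censored. The sentence must therefore be looking at data beyond her censoring date, and inclusion turns on a code recorded after her time at risk has ended.

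**Step 2. Starting figures for an illustration.** From Table 1, third annual report, E+P cohort: 89,438 person-years, 80 cancers and 399 hyperplasias. Printed 95% intervals at a true HR of 1.0: (0.48, 2.10) for cancer and (0.72, 1.39) for hyperplasia. The formula is HR × exp(±1.96 × √(1/d_D + 1/d_E)), where d_D and d_E are the Duavee and E+P events.

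Duavee person-years are not printed. The footnote's 10 months per user gives d_D = 5,400 × 10/12 × 80/89,438 = 4.03 for cancer and an interval of (0.37, 2.72). For hyperplasia it gives d_D = 20.08 and (0.64, 1.57). Neither matches the table. That is a separate matter, so I take d_D from the printed intervals instead:

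- Cancer: SE = ln(2.10/0.48)/3.92 = 0.3765; d_D = 1/(0.3765² − 1/80) = 7.74.
- Hyperplasia: SE = ln(1.39/0.72)/3.92 = 0.1678; d_D = 1/(0.1678² − 1/399) = 38.98.

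**Step 3. Equal loss in both cohorts.** The protocol gives no share of cases lost, so 10% to 75% is an assumed range. I also assume that the pilot counts were made without this rule (Section 7.5 mentions none) and that person-time hardly changes.

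| Share of cases lost | Cancer CI, HR = 1.0 | Hyperplasia CI, HR = 1.0 | E+P cancer per 1,000 person-years |
|---|---|---|---|
| 0% (as printed) | (0.48, 2.10) | (0.72, 1.39) | 0.89 |
| 10% | (0.46, 2.18) | (0.71, 1.41) | 0.81 |
| 25% | (0.43, 2.34) | (0.68, 1.46) | 0.67 |
| 50% | (0.35, 2.84) | (0.63, 1.59) | 0.45 |
| 75% | (0.23, 4.38) | (0.52, 1.93) | 0.22 |

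For example, at 50% the cancer events are 3.87 and 40, and √(1/3.87 + 1/40) = 0.532.

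**Step 4. Unequal loss.** Observed HR ≈ true HR × (share kept, Duavee)/(share kept, E+P).

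- Equal loss: ratio 1, so the HR is unchanged.
- Loss of 50% on Duavee and 25% on E+P: 0.50/0.75 = 0.67, so a true 1.5 appears as 1.00.
- Loss of 25% on Duavee and 50% on E+P: 0.75/0.50 = 1.50, so a true 1.0 appears as 1.50.

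Nothing in the protocol favours one of these over another.

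**The case against.** The strongest reply is that the authors plainly meant to censor. The abstract, Section 7.2.2 and the preceding sub-point all say so, and the parenthesis suggests that exclusion was meant only for undated surgery. That is probably the intent. It does not cure the text: the exception is worded as the only one, it requires a status code, and a programmer who follows it deletes the women in question. The reply does show that the repair is one of wording and needs no redesign.

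It is also fair to say that ending time at risk when the uterus is removed is sound, and that a case identified before surgery, for instance by biopsy, counts if the woman is kept. Only cases first identified on or after the surgery date are exposed to the censoring rule. How many there are depends on algorithms and event dates still to be fixed, with further detail deferred to a separate development plan (Appendix 3). That part of the point is conditional.

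A reader might go further and infer that the rule biases the HR downward and hides a Duavee risk. The documents do not support this. Suppose 90% of cancer cases have a hysterectomy, with a later status code in 50% of E+P and 35% of Duavee cases. Cases kept are 0.10 + 0.90 × 0.50 = 0.55 and 0.10 + 0.90 × 0.35 = 0.415, a ratio of 0.75. At 80% with a hysterectomy, the ratio is 0.48/0.60 = 0.80. All these inputs are invented. Swapping the cohorts gives 1.33 and 1.25, and equal status coding gives 1.0. Both cohorts are new initiators in the same database over the same period, and nothing shows that status coding differs between them.

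**Conclusion.** Wrong as written. Section 7.1 contradicts itself, the abstract and Section 7.2.2 on whether a dated post-index hysterectomy excludes or censors. Its literal rule conditions cohort entry on post-index information and removes recorded primary-endpoint cases. The contradiction rests on the text alone.

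The consequence is lower observed endometrial incidence and wider intervals, provided that hysterectomy is more common among cases than among other women. The HR is biased only if the loss differs between cohorts. The documents give neither the size nor the direction, so the figures above show scale under assumed losses and are not estimates. The possible loss from censoring at surgery is a secondary point that depends on the event-date definition. No planned sensitivity analysis would reveal either effect.

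**What to change.** Reconcile the abstract, Section 7.1 and Section 7.2.2 as follows.

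1. Exclude only for evidence of hysterectomy before the index date, or for a status code (V88.01 or V88.02, to agree with Appendix 2) with no earlier dated post-index procedure. State how codes on the same day are ordered.
2. Keep every woman whose post-index procedure is dated and not preceded by a status code. Censor her on the procedure date whether or not a status code follows.
3. For the two endometrial endpoints, state that an event identified on the procedure date, or from that surgery within a short prespecified window, counts as an event ahead of censoring.
4. Add a sensitivity analysis to Section 7.7.4 that varies the window.

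The cost is a few sentences and a small programming change. Items 1 and 2 remove the contradiction. Item 3 carries a small downside, since the window length is a judgement; item 4 shows how much it matters.
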